#### **ABBREVIATIONS**

AE Adverse event

ALP Alkaline phosphatase

ALT Alanine aminotransferase

BMI Body mass index

DMC Data monitoring committee eCRF Electronic case report form

ECG Electrocardiogram FAS Full Analysis Set

FoTA Final on Treatment Assessment

HbA1c Hemoglobin A1c
HFF Hepatic fat fraction
IA Interim analysis

MedDRA Medical Dictionary for Regulatory Activities

NAS NAFLD activity score

NAFLD Nonalcoholic Fatty Liver Disease NASH Nonalcoholic steatohepatitis

NASH CRN NASH Clinical Research Network

OC Observed cases

PBO Placebo

PCI potentially clinically important

PD Pharmacodynamic

QTcB QT Interval Corrected for Heart Rate using Bazett's Formula
QTcF QT Interval Corrected for Heart Rate using Fridericia's Formula

SAE Serious adverse event
SAP Statistical analysis plan
SOC System organ class

TEAE Treatment-emergent adverse event

TFLs Tables, Figures, and Listings
T2DM Type 2 Diabetes Mellitus
ULN Upper limit of normal

WHO World Health Organization

## 1. INTRODUCTION

This statistical analysis plan (SAP) is based on the approved final study Protocol SHP626-201 Amendment 4 dated 25 Aug 2017. The plan provides a technical and detailed elaboration of the statistical analyses of safety, tolerability, and efficacy of volixibat in adults with nonalcoholic steatohepatitis (NASH). The specifications for tables, figures, and listings (TFLs) will be included in a separate document.

On Jun. 6th, 2018, the Data Monitoring Committee (DMC) for the SHP626-201 study recommended that the study be terminated after determining that no dose of volixibat was effective based on the predefined interim analysis criteria set for week-24 MRI PDFF and ALT. On Jun. 7th, 2018, the Shire Unblinded DMC Recommendation Review Team (Unblinded DMC RRT) reviewed the IA data and concurred with the DMC recommendation of SHP626-201 study termination.

As a result of the termination of the SHP626-201 study, an abbreviated clinical study report (CSR) will be written based on the results of the statistical analyses planned within this SAP. This SAP will not be used for any other analyses.

## 2. STUDY DESIGN

Refer to study Protocol SHP626-201 Amendment 4 dated 25 Aug 2017 for details on study design.

## 3. STUDY OBJECTIVES

Refer to study Protocol SHP626-201 Amendment 4 dated 25 Aug 2017 for details on study objectives.

## 4. SUBJECT POPULATION SETS

#### 4.1 All Screened Set

The Screened Set will consist of all subjects who have signed an informed consent.

## 4.2 Randomized Set

The Randomized Set will consist of all subjects in the Screened Set who have been randomized into the study.

## 4.3 Safety Analysis Set

The Safety Analysis Set will consist of all subjects who take at least 1 dose of randomized IP, and have at least 1 post-baseline safety assessment (e.g., coming back for any visit, reporting of an AE or reporting the absence of AEs).

## 4.4 Full Analysis Set

The Full Analysis Set (FAS) will consist of all subjects in the safety analysis set who have at least 1 post-baseline efficacy assessment (e.g., MRI, liver biopsy, serum liver-related biochemistry measurement).

## 4.5 Interim Analysis Set

The Interim Analysis Set (IAS) will consist of all subjects in the safety analysis set who have both baseline and scheduled Week 24 efficacy assessment (MRI and ALT biochemistry measurement) at the data cut time of the IA.

## 4.6 Pharmacodynamic (PD) Analysis Set

The PD Set will consist of all subjects who receive the IP and for whom at least 1 post first dose PD blood sample is collected.

## 5. SUBJECT DISPOSITION

The number of subjects included in each subject set (i.e., Screened, Safety, Randomized, FAS, Interim, and Pharmacodynamic) will be summarized by treatment group.

A listing of all screen failures (i.e., subjects who were screened but not randomized) will be presented along with reasons for screen fail and details of any AEs.

The number and percentage of subjects who completed and prematurely discontinued during the study will be presented for each treatment group and overall for safety analysis set subjects. Reasons for premature discontinuation from the study as recorded on the termination page of the eCRF will be summarized (number and percentage) by treatment group for the safety analysis set. All subjects who prematurely discontinued from the study will be listed by discontinuation reason for the randomized set.

The number of subjects enrolled, randomized and completed will be tabulated by site and country. In addition, the duration of enrollment, in days, will be summarized for each site, country, and overall. Duration of enrollment will be calculated as (last date of contact for any subject at that site - the first date of informed consent for any subject at that site + 1).

A listing for subject disposition and study analysis sets will be produced for all randomized analysis set.

## 6. PROTOCOL DEVIATIONS

A full list of protocol deviations will be compiled and reviewed by the clinical team to identify key versus non-key deviations before final database lock. For deviations at study entry, patients will be assessed against the inclusion and exclusion criteria of the protocol. For on-study deviations, compliance with the protocol will be examined using blinded review of the database with regard to prohibited therapies, timing and availability of planned assessments. All protocol deviation data will be listed.

## 7. DEMOGRAPHIC AND OTHER BASELINE CHARACTERISTICS

Descriptive summaries of demographic and baseline characteristics will be presented by treatment group and overall for the Safety Analysis Set. Baseline will be determined using the last observation collected before the first dose of investigational product.

The following demographic and baseline characteristics will be summarized in the tables: age, gender, ethnicity, race, weight, height, BMI, BMI category (<18.5, 18.5 - 25, 25 - 30 and >=30), waist circumference, hip circumference, waist to hip ratio, smoking history, baseline T2DM, NAS = $\{6, 7, 8\}$  or NAS = $\{4, 5\}$ , NAS (4, 5, 6, 7, 8), NAS, individual NAS components (steatosis, lobular inflammation, ballooning), SAF score, individual SAF components (steatosis, ballooning, lobular inflammation), fibrosis score, magnetic resonance imaging (MRI) hepatic proton density fat fraction (PDFF), expanded balloon score, portal inflammation, megamitochondria, acidophil bodies, fibrosis location if  $\geq$  stage 2, steatosis zone, glycogenosis. Continuous variables will be summarized by descriptive statistics including number of subjects, mean, standard deviation (SD), median, minimum, and maximum. Categorical variables will be summarized by the number of subjects in each category and the percentage of subjects out of the total in the corresponding analysis set.

Age will be calculated as the difference between date of birth and date of informed consent, rounded down to the last whole year. In the cases where there is a partial date of birth, if only day of the month is missing then the day will be imputed as 15, if both the day and month are missing then the day will be imputed as 1 and the month will be imputed as 7 (July).

Height and weight will be collected and used to calculate BMI using the following formula:

$$BMI = \frac{Weight [Kg]}{[Height (m) * Height(m)]}$$

BMI should be rounded to 1 decimal place for reporting purposes.

Waist to hip ratio is calculated as waist measurement divided by hip measurement (waist (cm) / hip (cm)). Waist to hip ratio should be rounded to 2 decimal places for reporting purposes.

A listing will be created to show all the demographic and baseline characteristics for each Safety Analysis Set subject.

Medical history will also be listed for the Safety Analysis Set.

Smoking history will be listed for the Safety Analysis Set.

## 8. EXTENT OF EXPOSURE AND TREATMENT COMPLIANCE

## 8.1 Exposure to Investigational product

Exposure to double-blind investigational product for the Safety Analysis Set will be summarized with descriptive statistics (n, mean, SD, minimum, median, and maximum) and presented by treatment group. Exposure and compliance to investigational product will be listed for the Safety Analysis Set. The following will be calculated for the investigational product:

- Treatment duration, which is calculated as the number of days from the date of first dose of double-blind investigational product taken to the date of the last dose of double-blind investigational product taken, inclusively. Investigators are allowed to interrupt the study treatment to allow adverse events to resolve, if necessary. Any drug interruption will be subtracted off the treatment duration above to get the final treatment duration. Treatment duration will be presented as the number of weeks in the summary tables.
- Total dose, which is calculated as (total dispensed total returned) \* xxmg.
- The average daily dose will be calculated as total dose from above / duration of study drug exposure in days.

## **8.2** Measurement of Treatment Compliance

Investigational product dosing compliance for a specified period is defined as the total number of capsules actually taken by a subject during that period divided by the number of capsules expected to be taken during the same period multiplied by 100. The total number of capsules actually taken is calculated by the total number of capsules dispensed minus the number of capsules returned. If a blister pack is not returned, the number of capsules returned for that blister pack will be imputed to zero. The number of capsules expected to be taken is calculated as the number of days that subject was in the particular period multiplied by the number of capsules to be taken per day during that period. The investigational treatment compliance over the entire study will be therefore calculated using the formula:  $100 \times [(total)]$ 

number of capsules dispensed) – (total number of capsules returned)]/ (total number of capsules planned to be taken per day  $\times$  duration of study drug exposure in days). The investigational treatment compliance will be categorized as < 80, 80-120, and > 120% and the number and percentage of patients in the Safety Analysis Set will be presented by treatment group.

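### Every capsule in an unreturned blister pack is counted as taken, so compliance, and apparently dose, can be overstated but not understated

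*SAP*

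**What the plan says.** SAP section 8.2 defines the numerator of compliance: "The total number of capsules actually taken is calculated by the total number of capsules dispensed minus the number of capsules returned". For a missing pack it adds: "If a blister pack is not returned, the number of capsules returned for that blister pack will be imputed to zero". Over the whole study the denominator is the planned capsules per day times the days of study drug exposure. "The investigational treatment compliance will be categorized as" below 80, 80 to 120 and above 120 percent, and is tabulated by treatment group.

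Section 8.1 runs treatment duration from the first dose "to the date of the last dose of double-blind investigational product taken, inclusively", and then: "Any drug interruption will be subtracted off the treatment duration above to get the final treatment duration". I take this net duration to be the exposure duration used in section 8.2. In the same section, "Total dose, which is calculated as" the dispensed total less the returned total, times the capsule strength. Average daily dose divides that by the exposure days. Section 8.1 has no rule of its own for packs that do not come back.

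The SAP plans no alternative calculation, no missing category for compliance and no count of subjects with unreturned packs.

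**The concern.** A missing pack shows neither that its capsules were swallowed nor that they were not. The rule settles the doubt one way only: full use. For a subject who stops partway through a pack and keeps it, the numerator says the whole pack was taken while the denominator says dosing ended earlier. Both can be true only if the subject took more than planned, so the above-120 category can fill with subjects who did nothing of the kind. In a poorly adherent subject the same rule can lift compliance from below 80 into 80 to 120, where nothing looks odd.

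At stake is how the abbreviated study report describes the dosing actually received. The SAP records that the study ended because no dose was judged effective, and a reader of that report will want to know whether subjects took the drug.

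**Working it through.** The SAP gives no compliance figure to reproduce, so this applies its own formula.

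**Inputs from the SAP.** Compliance % = 100 × (dispensed − returned) / (capsules per day × exposure days), with returned = 0 for an unreturned pack (section 8.2). Exposure runs from first to last dose less interruptions (section 8.1). Visits fall on days 14, 28, 56, 84, 168, 252 and 336 (Appendix 1).

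**Assumptions not in the SAP.** One capsule a day. For early stoppers, supply at each visit covers exactly the time to the next visit, in one pack, and only the last pack is unreturned. For the completer, 12 packs of 28 capsules.

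**Direction.** If an unreturned pack held L unused capsules, compliance rises by 100 × L / exposure days. This is zero for an emptied pack and positive otherwise, never negative. With L = 28:
- 28 days of exposure: 28/28 = +100 points
- 84 days: 28/84 = +33.3 points
- 168 days: 28/168 = +16.7 points
- 336 days: 28/336 = +8.3 points

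**Fully adherent subject, stops on day 98.** Supply to day 168 is 168 capsules. The last pack holds 84, of which 98 − 84 = 14 were taken and 70 were left.
- True: 98/98 = 100%
- As the SAP scores it: 168/98 = 171.4%
- None of the unreturned pack counted: 84/98 = 85.7%

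The 85.7% is the lower bound that accountability data can give, because the 14 capsules taken from the kept pack cannot be seen. The true 100% lies between the bounds. Total dose is overstated by 70/98 = 71.4%, if section 8.1 uses the same counts.

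**Subject taking 75%, stops on day 98.** Taken from returned packs: 0.75 × 84 = 63. As scored: (63 + 84)/98 = 150%, against a true 75%.

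**Completer, 336 days.** Nine packs returned with 85% use: 9 × 28 × 0.85 = 214.2 capsules. Three packs unreturned, half used: 3 × 28 = 84 dispensed, 42 taken.
- True: (214.2 + 42)/336 = 76.25%, below 80
- As scored: (214.2 + 84)/336 = 88.75%, in 80 to 120
- None taken: 214.2/336 = 63.75%
- Unreturned packs dropped from numerator and denominator: 214.2/252 = 85%, still in the wrong category

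**Stop day alone does not set the size.** A fully adherent subject stopping on day 63 scores 84/63 = 133.3%, less than the later stopper on day 98, because the supply interval after day 84 is longer and leaves more capsules over.

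**Missing last-dose date.** Section 14.5 substitutes the last visit at which product was returned. If that is day 84 and the next 84 capsules never come back, the score is (84 + 84)/84 = 200% for a subject fully adherent to day 84.

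**The case against.** The strongest reply is that little hangs on this. Section 1 limits the SAP to an abbreviated report, section 10 plans no inferential safety analysis, and no analysis set in section 4 depends on compliance. Treatment duration is built from dates and the pack rule does not touch it. Section 8.1 lists exposure and compliance by subject and Listing 5.1 covers accountability, so implausible values may be traceable. All of this stands and keeps the severity low. It does not correct the summary tables.

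The rule is also correct for a pack that was emptied and thrown away. That stands too: the error needs leftover capsules.

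A reader might infer more than the document supports:
- That early termination made the problem common. Stopping mid-pack does no harm if the pack is returned; the SAP provides for early termination visits and gives no return rates.
- That non-return is concentrated in subjects who dropped out, or that arms with more discontinuation are more biased. Either is possible, but the SAP has no data on it.
- That extreme values such as several hundred percent are typical. Pack size and dispensing amounts are not stated, so such figures depend wholly on the supply assumed.
- That the dose summaries are certainly affected. The imputation sentence stands only in section 8.2; carry-over to section 8.1 is inferred from the shared quantity and the absence of another rule.

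**Conclusion.** The point holds as a low-severity one. The rule can push compliance up and never down, wherever an unreturned pack still held capsules. For a given number of leftover capsules the overstatement is larger with shorter exposure. Total dose and average daily dose probably share it. Under the stated supply assumptions it turns a true 100% into 171.4% for a day-98 stopper, and a true 76.25% into 88.75% for the completer, each with a change of category. These are illustrations, not estimates for this trial: the frequency of unreturned packs, their remaining content and any imbalance between arms are unknown. Only descriptive outputs are affected, and no planned test or analysis set would change.

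**What to change.** Keep the present calculation but label it as the upper bound, with all unreturned capsules counted as taken. Add the lower bound, with none of them counted as taken, for compliance, total dose and average daily dose. In the examples the compliance bounds are 63.75% to 88.75% for the completer and 85.7% to 171.4% for the day-98 stopper. State in section 8.1 that the same handling applies there.

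Show by treatment group the number of subjects with at least one unreturned pack and the number whose compliance category differs between the bounds. If both are small, the matter is closed. Both examples above would be flagged.

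Do not make exclusion of unreturned packs the main estimate. It assumes they were used like the returned ones, and it leaves the completer at 85% against a true 76.25%.

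The cost is a few sentences in the SAP, a little programming and a less tidy table. For a subject whose only pack is unreturned the lower bound is 0%, which cannot be literally true for someone in the Safety Analysis Set, but it shows correctly that the pack count says nothing about that subject.

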## 9. PRIOR AND CONCOMITANT MEDICATION AND THERAPIES

Version WHODRUG Jun\_2016\_DDE (Enhanced) of the World Health Organization (WHO) drug dictionary will be used to classify prior and concomitant medications and therapies by therapeutic class.

Prior medication/therapy is defined as any medication/therapy received within 30 days of the date of first dose of investigational product. Concomitant medication/therapy is defined as all treatment taken between the dates of the first dose of the IP and the end of the follow-up period, inclusive. Any medication with a start date after the end of follow-up period will not be considered a concomitant medication.

All prior, concomitant medications and therapies will be listed.

.

## 10. SAFETY ANALYSES

The safety analysis will be performed by treatment using the safety analysis set. Safety variables include AEs, clinical laboratory variables, vital signs, and ECG variables. For each safety variable, the last value collected before the first dose of double-blind investigational product will be used as baseline for all analyses of that safety variable. A Final on-Treatment Assessment (FoTA) will be defined as the last valid assessment obtained after Baseline and whilst on investigational product and will be summarized in addition to all scheduled visits.

No inferential statistical analyses of safety endpoints will be performed.

#### **10.1** Adverse Events

Adverse events will be coded using Version 19.0 of the Medical Dictionary for Regulatory Activities (MedDRA).

An AE (classified by preferred term) that occurs during the Double-blind Evaluation Phase or Follow-up Phase will be considered a TEAE if it has a start date on or after the first dose of double-blind investigational product and no later than the follow-up visit, or it has a start date before the date of the first dose of double-blind investigational product, but increases in severity on or after the date of the first dose of double-blind investigational product and no later than the follow-up visit. If more than 1 AE with the same preferred term is reported before the date of the first dose of double-blind investigational product, then the AE with the greatest severity will be used as the benchmark for comparison to the AEs occurring during the Double-blind Evaluation Phase or Follow-up Phase under the preferred term.

An overall summary of the number of subjects with TEAEs will be presented by treatment, including the number and percentage of subjects and absolute count of events for:

- Any TEAE,
- Any serious TEAE,
- Any TEAE related to investigational product in the opinion of the investigator,
- Any serious TEAE related to investigational product in the opinion of the investigator,

- Any TEAE leading to withdrawal of investigational product,
- Any severe TEAE,
- Any related severe TEAE
- Any TEAE leading to death

The number and percentage of subjects reporting TEAEs in each treatment group will be tabulated in the following ways:

- By System Organ Class (SOC) and preferred term;
- By Preferred term
- By SOC, preferred term, and maximum severity,
- Serious TEAEs by SOC and preferred term,
- TEAEs related to investigational product in the opinion of the investigator by SOC and preferred term
- TEAEs leading to withdrawal of investigational product (IP) by SOC and preferred term

If more than 1 AE occurs with the same preferred term for the same subject, then the subject will be counted only once for that preferred term using the most severe and most related occurrence for the summarization by severity and by relationship to investigational product. The overall frequency will be considered for sorting purposes for the tables with SOC and PT.

In addition, for treatment emergent Diarrhea AEs the following will be summarized by treatment group: relative onset day, counts and percentages of events per subject, events treated with medication, outcome, drug withdrawn, duration of individual events (in days), duration of individual events treated with medication (in days), duration of individual events not treated with medication (in days), severity of diarrhea AEs, and worst severity of diarrhea AEs.

The incidence and prevalence of treatment emergent Diarrhea AEs will be summarized and plotted by study week for each treatment group. In addition a figure of all Diarrhea AEs over time will be presented displaying the severity of AEs, duration of AEs, and medication given.

All information about AEs collected on the eCRF will be listed alongside the treatment, preferred term, and SOC. For Serious AEs, deaths, AEs related to the investigational product, and TEAEs leading to study discontinuation, a separate listing will also be provided.

## 10.2 Clinical Laboratory Variables

Descriptive statistics for clinical laboratory values (in SI units) and changes from baseline at each post-baseline visit and at the FoTA visit for quantitative variables will be presented by treatment group for the clinical laboratory parameters in Table 1. A summary of liver enzyme elevations at each post-baseline visit, the FoTa visit, and overall post-baseline will be presented by treatment group for AST, ALT, and total bilirubin. The clinical laboratory test results will be listed for all subjects. The Evaluation of Drug Induced Serious Hepatotoxicity (eDISH) graph will also be provided for total bilirubin vs. ALT. Each point in the figure should represent a unique subject's peak serum ALT and peak serum total bilirubin (TB) values. Peak serum ALT is shown along the x-axis and peak TB is shown along the y-axis as x-fold upper limits of normal (ULN) on a log scale. The individual subject time course of ALT, AST, ALP, GGT and Total Bilirubin for Subjects with a Post-baseline ALT > 3xULN or Total Bilirubin > 2xULN will also be presented graphically (Figure 4.6.9.1). Subjects with Liver Enzyme Elevations: AST, ALT, ALP, GGT and Bilirubin will also be listed.

